### **Study time**

About 35 to 40 patients with metastatic NET are treated annually at the A.C.Camargo Cancer Center. Therefore, we estimate to recruit the study population in a maximum period of 2 years and have the first assessment in 3 years.

### **Ethical Considerations**

The study will be carried out in accordance with the protocol, the Good Clinical Practice guidelines of the International Harmonization Conference (ICH GCP) and the applicable local laws and regulatory requirements. The informed consent form (IC) must comply with ICH GCP guidelines, local regulatory regulations and legal requirements.

The investigator must ensure that each patient in the study, or their legal representative, is fully informed about the nature and objectives of the study and possible risks associated with participation. The investigator will obtain written consent from each patient before any specific study activity is performed. The investigator will retain one copy of each consent form signed by the patient. It will be emphasized that participation is voluntary, and that the patient has the right to refuse participation or leave in the middle of the study whenever he wishes. This will not affect subsequent patient care. Female patients will be instructed not to become pregnant during treatment, being

instructed to use contraceptive methods if they are of childbearing age, as has been done in the routine. There is a risk of loss of confidentiality, if patient data is identified, however, all reasonable measures will be taken to prevent this from happening.

The protocol will be approved by the Local Ethics Committee. The study will be registered with the international clinical trial registration database ClinicalTrial.gov.

### **Study Funding and Sponsorship**

The patient will not incur any costs in relation to the MIBG-I scintigraphy exam or treatment with MIBG-I, which will be paid for by the Brentani Prize and will be carried out at the Dept. Nuclear Medicine, under the supervision of [name]. Everything else (laboratory tests, hormone dosages produced by TNE, conventional imaging tests, medical consultations) is not part of this protocol as it is already part of the routine treatment of patients with NET at the A.C.Camargo Cancer Center, both in the Unified Health System and in the supplementary/private health sector. For this study, insurance against risks of serious adverse events and / or requiring medical intervention (complementary exams, hospitalization or emergency at A.C.Camargo Cancer Center) will be contracted due to an adverse event related to treatment with MIBG-I.

### **Global innovation potential and for A.C.Camargo Cancer Center**

PRRT therapies have been shown to be highly effective in NET and today they are an active area of research with the development of new radiopharmaceuticals. There is a scientific rationale to test MIBG-I prospectively and with an adequate methodology, in addition to assessing the impact on patients' quality of life for the first time. If the study is positive, it has the potential to change national and international guidelines for the treatment of NET, helping many patients and giving visibility to the institution. In addition, the incorporation of MIBG-I as a therapeutic strategy in the treatment protocols for NET in the A.C.Camargo Cancer Center will allow that, after the study, the institution will be able to offer MIBG-I to supplementary health patients, recovering the costs invested in the study MIBNET.

### **Potential for cost-effectiveness**

Treatment with MIBG-I, in addition to being available at SUS for the treatment of patients with PggF, appears to offer significant disease control for patients with NET. If the study is positive, it can be cost-effective, as we estimate that 67% of patients will obtain disease control lasting at least 12 months, which will provide time free of toxic therapies, with a low level of evidence and costly to patients and paying sources. In addition, in the absence of a clinical study, these toxic and ineffective therapies are used sequentially, so that each patient will do, in the period of 12 months, at least two of them.

**Table 1.** Treatments used in midgut NET or refractory lung, respective toxicities, efficacy and levels of scientific evidence

Treatment	Disease control rate (%)	Time of disease control (months)	Common toxicities	Evidence level
Folfox/Capox	0-10%	4 – 6	Peripheric neuropathy, diarrhea, nausea, vomiting, thrombocytopenia, anaemia	Retrospective, heterogeneous population*
Capecitabine/ Temozolomide	0-10%	4 – 6	Nausea/Vomiting, diarrhea	Retrospective, phase 1/2 with heterogeneous population
Interferon alpha (3 to 6 million units/week)	20 – 30% (symptoms), 50% (radiological)	10	Psychiatric disorders, immunes, fatigue, myopathy, myelosuppression	Phase III for radiological control, retrospective studies for symptomatic control
Debulking hepatic surgery (R2)	50 – 90% (only symptoms)	19 – 45	Surgical risk compared to a hepatectomy	Retrospective, heterogeneous population
MIBG- 	63 – 80%	12 – 24	Myelosuppression	Retrospective, heterogeneous population

\* neuroendocrine tumors of different origin, efficacy measured with distinct criteria

**TABLE 2.** Complete procedural summary of the study after signing the informed consent form

Procedure	Screening *	Baseline evaluation	D1 **	S2 **	S4 **	...	S8 **	S12 **	S16 **	...	S24 **	Every 12 or 8 weeks
Eligibility assessment												
MIBG scan	X											
Demographics, medical history and previous treatment	X											
Therapeutic MIBG												
200mCi MIBG-  I IV administration			X				X		X		X	
Clinical safety assessment												
Physical exam		X	X	X	X	X	X	X	X	X	X	X
Vital signs, body weight and ECOG		X	X	X	X	X	X	X	X	X	X	X
Signs and symptoms assessment		X	X	X	X	X	X	X	X	X	X	X
Adverse Event Assessment		X		X	X	X	X	X	X	X	X	X
Laboratory safety assessment												
Hemogram	X	X	X	X	X	X	X	X	X	X	X	
Urea/creatinine	X	X	X	X	X	X	X	X	X	X	X	
Bilirubin, AST/ALT	X	X	X	X	X	X	X	X	X	X	X	
NA, K	X	X	X	X	X	X	X	X	X	X	X	
Pregnancy test in women of childbearing age		X										
Image assessment												
CT of lung, abdomen and pelvis ***	X							X			X	X
Tumor marker **												
Specific hormone		X						X			X	X
Quality of life **												
EORTC QLQ-C30		X						X			X	X
EORTC QLQ-GINET21		X						X			X	X

IV, intravenous; MIBG, metaiodobenzylguanidine

\* within 6 weeks of the first dose and within 4 working days of D1;

\*\* window of +/- 3 days

\*\*\* baseline tests within 8 weeks of D1; Resonance of the abdomen and pelvis in special cases (allergy to iodinated contrast); window +/- 5 days

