MIBG-I is administered at a dose of 200mCi intravenously every 8 weeks for up to 4 cycles. Laboratory tests are performed every 15 days, with a focus on assessing myelotoxicity. Laboratory blood tests within the appropriate results (see “inclusion criteria”) allow the administration of the next cycle. In the case of any toxicity with a degree equal to or greater than 3 or intolerable and persistent grade 2 toxicity, the next course of treatment will not be administered until the toxicity is grade 1 or resolves. If the toxicity does not resolve or becomes grade 1 within 8 weeks, the next cycle is not administered, and treatment is stopped.

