### **Security Assessments**

#### **Baseline Assessments:**

After signing the informed consent form, patients will be submitted to the baseline eligibility assessment (see Table 2).

Within 6 weeks of the first treatment dose: search for noraepinephrine expression by MIBG-I scintigraphy. If positive, eligibility is confirmed, and the following procedures are:

- Within 4 days of D1C1: Medical history, including previous diagnosis and treatment, history of other diseases (active and resolved), medications in use and general demographic data. Complete physical examination, ECOG performance index (PS) and vital signs.
- Within 4 days of the first treatment dose, laboratory tests will be performed: blood count, urea, creatinine, ALT, AST, total bilirubin, sodium, potassium, and pregnancy test for women of childbearing age; these patients will be oriented to contraception.
- Baseline imaging exams performed within 8 weeks of the first treatment dose will be accepted: CT scan (or MRI, if applicable) of the abdomen, pelvis and chest.
- For patients with functioning NET, it will be accepted that baseline tumor marker exams have been performed within 8 weeks of the first treatment dose (eg 5HIAA in 24-hour urine).

With the exception of MIBG scintigraphy, which is used routinely for patients with PggF (but not TNE), all of the above tests are already part of the routine in the treatment of NET at A.C.Camargo Cancer Center.

*Safety assessments during treatment:*

Patients will be evaluated clinically and with laboratory tests (Table 2) every 15 days between treatment cycles and after completion until resolution of any adverse treatment effects. +/- 3 days window will be allowed.

- Complete physical examination, measurement of vital signs, weight measurement, ECOG, use of medications.
- Assessment of adverse events.
- Laboratory evaluation: blood count, urea, creatinine, ALT, AST, total bilirubin, sodium, potassium, and others, if clinically indicated.

To grade toxicities we will use the CTCAE 5.0 criteria. Patients who have intolerable grade 2 or grade 3 toxicity that the investigator deems to be related to MIBG-1131 will have their treatment cycle delayed to grade 1 or resolution. If there is no reduction in the intensity of the adverse event to grade 1 within 8 weeks, treatment is discontinued.

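### Pregnancy is an absolute contraindication to MIBG-I131, yet the only scheduled pregnancy test is before dose 1 and none is required before doses 2 to 4

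*Combined protocol and SAP*

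**What the plan says.** Pregnancy and lactation are exclusions (Exclusion Criteria) and stand among the absolute contraindications in the section Treatment with high-dose MIBG-I131. That section also cites teratogenic potential and asks for contraception during treatment and for some months afterwards.

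The drug "is administered at a dose of 200mCi intravenously every 8 weeks for up to 4 cycles". Table 2 places the doses at D1, S8, S16 and S24. The Study design section instead sets a minimum gap of 60 days and says that most patients at the centre receive 3 or 4 cycles.

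The pregnancy test appears in two places, which agree:

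- In Table 2, the row "Pregnancy test in women of childbearing age" is marked once, under the baseline evaluation.
- In Baseline Assessments, "Within 4 days of the first treatment dose, laboratory tests will be performed", and the list ends with a "pregnancy test for women of childbearing age; these patients will be oriented to contraception".

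For the treatment period the plan says:

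- "Patients will be evaluated clinically and with laboratory tests (Table 2) every 15 days between treatment cycles".
- "Laboratory evaluation: blood count, urea, creatinine, ALT, AST, total bilirubin, sodium, potassium, and others, if clinically indicated".
- "Laboratory tests are performed every 15 days, with a focus on assessing myelotoxicity".
- "Laboratory blood tests within the appropriate results", judged against the inclusion criteria, release the next cycle.

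**The concern.** Before dose 1 the plan does not rely on contraception advice alone: it also requires a test. Doses 2 to 4 carry the same activity and the same contraindication, but no test is scheduled for them.

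A recognised pregnancy would stop dosing at any cycle, so the gap is one of detection. A pregnancy that begins after the baseline test and is still unrecognised could pass every written check, and the woman would then receive 200 mCi of a drug that the protocol itself describes as potentially teratogenic. The harm would be serious and irreversible. This is a patient-safety point; it does not touch the endpoints, the sample size or the analysis.

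**Working it through.** The plan states no figure to reproduce. The check is whether any written provision requires a pregnancy test before a later dose, followed by the age of the baseline result at each dose.

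**Provisions that could require a test before doses 2 to 4**

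| Place | Content | Test required? |
|---|---|---|
| Table 2, pregnancy row | One mark, at baseline | No |
| Safety assessments during treatment, laboratory list | Eight named items, plus others if clinically indicated | No |
| Next-cycle rule, Treatment with high-dose MIBG-I131 | Blood results judged against the inclusion criteria, which cover liver enzymes, bilirubin, neutrophils, platelets, hemoglobin and creatinine clearance | No |
| Criteria for suspension of treatment | Pregnancy not listed | No |
| Administration protocol, on admission | History, and control exams that are not itemised | Not stated |
| Contraception and pregnancy advice (three treatment and baseline sections, and Ethical Considerations) | Advice and instruction | No |

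Scheduled tests before doses 2 to 4: 0 of 3. The single mark is not a table-reading artefact, because the Baseline Assessments text gives the same timing.

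**Age of the baseline result at each later dose**

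Inputs: test at most 4 days before dose 1 (Baseline Assessments); spacing of 8 weeks, which is 56 days (Treatment with high-dose MIBG-I131, Table 2), or a 60-day minimum (Study design); window of +/- 3 days (Table 2 footnote).

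Formula: age at dose k = (k − 1) × spacing + window + 4.

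| Schedule | Dose 2 | Dose 3 | Dose 4 |
|---|---|---|---|
| Exact 8 weeks | 56 + 4 = 60 | 112 + 4 = 116 | 168 + 4 = 172 |
| 8 weeks, +3 days | 56 + 3 + 4 = 63 | 112 + 3 + 4 = 119 | 168 + 3 + 4 = 175 |
| 60-day minimum | 60 + 4 = 64 | 120 + 4 = 124 | 180 + 4 = 184 |

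The 56-day and 60-day schedules conflict within the protocol, so both are shown. None of these values is a ceiling: Study design sets only a minimum interval, and the toxicity rule allows a wait of up to 8 weeks before treatment is stopped.

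**Extra tests if the gap is closed:** 4 doses − 1 already tested = 3 per eligible woman at most.

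**The case against.** The strongest reply accepts the text and disputes the weight.

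- **Practice may already cover it.** Treatment takes place at one centre under national nuclear standards and institutional routine. On admission for dosing, patients give a history and have control exams that the protocol does not itemise; these may include a pregnancy test. This stands as a limit on what can be said about practice. It does not supply a written requirement.
- **Other safeguards exist.** Contraception is advised, patients are instructed not to become pregnant, clinical review takes place about every 2 weeks, and extra tests are allowed when indicated. These reduce the risk. But an indicated test needs prior suspicion, an early pregnancy may cause no symptoms, and the protocol lists mild nausea and fatigue as expected drug effects, so such symptoms could be put down to treatment.
- **Few women may be affected.** With 22 patients and no stated sex or age distribution, the number could be zero. This stands.
- **Days since the test are a loose measure of risk.** This also stands. A pregnancy that began soon after baseline would meet several clinical visits before doses 3 and 4, so the rising figures do not mean a rising risk of an unnoticed pregnancy. They show only that the baseline result is too old to be informative at any later dose.
- **Table 2 visits can drift from the actual doses.** At the 60-day minimum, doses 3 and 4 fall on days 120 and 180, while S16 and S24 with +3 days end on days 115 and 171: 5 and 9 days earlier. This is a reason to tie the test to the dose date, not a reason to omit it.

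**Conclusion.** The concern holds. Followed as written, the plan would release doses 2, 3 and 4 without a pregnancy test, relying on a result up to 60, 116 and 172 days old at 8-week spacing, or 64, 124 and 184 days old at the 60-day minimum. These ages assume that the baseline test is done the full 4 days before dose 1 and that no dose is delayed.

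Confidence is high that no written requirement exists. What the site does in practice, and how many women are affected, cannot be judged from the protocol. The event is unlikely, but its consequence is grave and prevention costs very little, so the protocol should be corrected.

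**What to change.** For women of childbearing potential:

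1. In Table 2, mark the pregnancy row at S8, S16 and S24.
2. Add the test to the on-treatment laboratory list under Safety assessments during treatment, timed to the actual dose date, for example within 4 days before the dose as for dose 1, so that it moves with any delay.
3. In the next-cycle rule under Treatment with high-dose MIBG-I131, add one sentence that requires a negative result before the dose is released.

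The investigators can choose the type of test. If the admission control exams already include one, the change is only to write that down.

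The cost is three table marks, one list item, one sentence and at most three inexpensive tests per eligible woman who receives all four doses. No visit need be added, since the sample can be taken with the 15-day laboratory tests when one falls close enough to the dose, or otherwise at the dosing admission. A positive or unclear result would hold the dose until resolved, which is compatible with a design that sets only a minimum interval.
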